Concerns and wellbeing	MYCaW (self-identified concerns and wellbeing)	continuous	Patient and family member	T _{1-T₂} T _{1-T₃}
Post-treatment regret	"Looking back, is there anything about your treatment that you would do differently?"	Binary	Patient and family member	T ₃
Patient – psychological wellbeing, PROMIS	Psychosocial Illness Impact-Neg 4a Psychosocial Illness Impact-Pos 4a Anxiety 4a*	continuous continuous continuous	Patient	T ₂ T ₃
Family – psychological wellbeing, PROMIS	PROMIS SF Global Health Anxiety 4a	continuous continuous	Family member	T ₂ T ₃
Treatment received	Total number of operations scheduled after visit with surgeon Total number of operations scheduled and performed	count; 0-3 count; 0-3	Chart review	T ₀ T ₃

* Items in **bold** are **primary outcomes**.

T₀: Audio recorded clinic visit between patient, family member and surgeon

T₁: Phone questionnaire with patient and family member 24-48 hours after visit with surgeon

T₂: Questionnaire 1-2 weeks post-surgery or, for patients who do not have surgery, 6-8 weeks post initial visit

T₃: Questionnaire and chart review 6-8 weeks post-surgery or, for patients who do not have surgery, 12-14 weeks post initial visit

Blinding

Although we cannot blind surgeons to intervention group, based on the need for them to endorse use of the QPL during clinic visits, they will not be informed of the outcomes measured in this study. Patient and family member participants will be told that the study goal is to evaluate surgeon-patient communication and will be blinded to objectives regarding testing of the QPL intervention. We expect negligible contamination between patient participants in different study arms as the intervention requires surgeon endorsement of the QPL with a letter from the patient's surgeon and the surgeons work in different clinics on different days. Although patients in the control arm may access question lists from outside sources, we know from previous research that surgeons do not routinely ask patients about such instruments.

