The goal of evaluating MYCaW is to test how much participant-reported concerns change over time for patients who did and did not receive the QPL. Our understanding of the MYCaW measure evolved since the start of the study based on the blinded coding of MYCaW data which revealed a much wider range of problems and concerns in response to MYCaW items than our previous and current review of the literature would suggest. Because not all patients in our study will plan to have surgery after meeting with a surgeon, there is heterogeneity in the description of concerns that is dependent on their treatment plan. Without changing our pre-specified analytic plan, we believe we will have findings that are extremely difficult to interpret. Furthermore, if an effect (positive or negative) of the intervention is identified, it would be challenging to assist surgeons and patients in using these results as many different types of concerns will be lumped together. These proposed changes are responsive to the data and the setting of this trial.

As such, we will conduct a stratified analysis based on the post-randomization variable of a treatment plan to have surgical intervention as determined by the T0 conversation with the surgeon. To this end, our analysis will exclude patients whose treatment plan did not include surgery upon leaving the surgical consultation at T0, and whose treatment plan was unclear at the end of the T0 consultation (this corresponds to categories #2 and #3 below regarding the “treatment plan”).

Within the cohort of patients whose treatment plan includes surgery, we will compare intervention to control patients who noted similar concerns. We will first categorize participants (both patients and family members) by the primary (first) concern expressed and then compare the respondent-reported rating of that concern, assessing the mean score between treatment groups for each category. We will next separate respondents by type: patient and family and repeat this analysis. We will also compare the change of the respondent’s (patient or family member in separate groups) rating of that concern between T1 and T2 using a respondent-level random effects model. We will similarly analyze the change between T1 and T3.

Secondary outcomes: Aim-1: patient engagement [PEPPI-5, OPTION5, HCCQ]

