We met regularly for 10 months with a dedicated group of patients and family members to design a QPL specifically targeting the preoperative decisional needs of patients considering high-risk surgery.⁴² Our research group gathered over 300 questions from publicly available 'questions to ask your surgeon' and focused on three patient-mediated targets identified by our patient and family advisors: 'Should I have surgery?', 'What should I expect if everything goes well?', and 'What happens if things go wrong?' (figure 1). We discarded questions that were either redundant or irrelevant to these targets and used feedback from our patient, family, surgeon and hospital stakeholders to refine the list to create a surgical QPL brochure containing 11 questions. Details of the QPL development have been previously published.⁴²

Theoretical framework underlying the QPL intervention

Based on the theories of self-determination⁴³ and relational autonomy^{44 45} described by Elwyn *et al*,⁴⁶ QPLs aim to overcome structural and interactional barriers and promote patient activation, thereby increasing patient engagement in decision making. Given the transactional nature of the patient experience,⁴⁷ activated patients will receive more patient-centred care and take part in more collaborative decision making, even within the same provider. By supporting patients' need for autonomy and relatedness, interventions — such as a QPL — to help patients gain knowledge about treatment options offer a strategy to promote patients' self-perceived capacity to engage in treatment decisions.⁴⁸

Randomised comparative effectiveness study

Our intervention consists of the surgical QPL and a brief letter from the surgeon endorsing its use, mailed to the patient in advance of the clinic appointment. The intervention targets patients and family members in the preoperative period and seeks to impact (1) patient engagement in decision making for high-risk surgery,

Table 1 Stepped wedge study design: 40 surgeons at five sites

Wave	Portland	Newark	Boston	San Francisco	Madison	Total
0	0	0	0	0	0	0
1	2 (2)	1 (1)	2 (2)	1 (1)	2 (2)	8
2	3 (1)	3 (2)	3 (1)	3 (2)	4 (2)	16
3	4 (1)	4 (1)	5 (2)	5 (2)	6 (2)	24
4	5 (1)	6 (2)	6 (1)	7 (2)	8 (2)	32
5	6 (1)	7 (1)	8 (2)	9 (2)	10 (2)	40
Total number of patients per site*	72	84	96	108	120	480

*Half of all patients will have received the question prompt list intervention by the end of wave 5, for a final sample size of 240 patients in each study arm.

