We selected psychological well-being as an important outcome based on feedback from our patient and family stakeholders who reported significant emotional harm; specifically they felt 'blindsided' when surgical results did not match their expectations. The primary outcome measures to assess psychological well-being are the

Measure Yourself Concerns and Wellbeing (MYCaW) and patient-reported post-treatment regret. MYCaW is a patient-reported outcome measure originally designed for patients with cancer and their family members, which we have adopted for use with patients who have vascular disease. MYCaW allows patients and family members to identify their own most pressing health concerns and rate their well-being. We will administer the MYCaW at the three time points. Patients and family members will report their initial responses to the MYCaW at the time of the first questionnaire, 24–48 hours after the clinic visit. Participants will independently rescore their initial concerns and well-being at the two subsequent time points corresponding to the second and third questionnaires; the difference in scores describes improvement or deterioration in their well-being. To assess treatment-associated regret, we will ask patients and family members at the time of the third and final questionnaire — 'Looking back, is there anything about your treatment/your family member's treatment that you would do differently?' — and transform responses into a dichotomous variable (regret, no regret) for analysis.⁵⁵ We will also analyse these responses qualitatively.

Secondary outcome measures include validated measures from the Patient-Reported Outcomes Measurement Information System (PROMIS) to assess the psychological impact of illness from the patient's perspective.⁵⁶ Patients will receive the Psychosocial Illness Impact-Neg 4a, Psychosocial Illness Impact-Pos 4a and Anxiety 4a; family members will be asked to complete Anxiety 4a and PROMIS short form (SF) Global Health. Because studies of other interventions that support shared decision making show that in some situations informed patients elect more conservative treatment,⁵⁷ we will compare the total number of operations scheduled and performed on enrolled patients by their study surgeon between the control and intervention groups. We will also collect information about potential mediating variables and covariates described in table 3.

Aim 3: postoperative conflict

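### MYCaW ratings are compared between arms within the concern that respondents name first at T1, a second post-exposure stratifier about which the plan gives no caution

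*Combined protocol and SAP*

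**What the plan says.** The SAP section *Stratified Analysis: Aim-2 MYCaW* first restricts the analysis to patients who left the T0 visit with a plan for surgery. Within that cohort, "we will compare intervention to control patients who noted similar concerns". The steps are then given: "We will first categorize participants (both patients and family members) by the primary (first) concern expressed", and the ratings are then compared by "assessing the mean score between treatment groups for each category". Patients and family members are pooled at this step and separated afterwards. Changes in the rating of that concern from T1 to T2 and from T1 to T3 follow, with a respondent-level random effect.

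The timing is set out elsewhere:

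- Published protocol, *Randomised comparative effectiveness study*: the QPL and the surgeon's letter are "mailed to the patient in advance of the clinic appointment".
- SAP, notes to Table 1: T1 is a "Phone questionnaire with patient and family member 24-48 hours after visit with surgeon".
- Published protocol, *Aim 2: psychological well-being*: "Patients and family members will report their initial responses to the MYCaW at the time of the first questionnaire". On later occasions, "Participants will independently rescore their initial concerns and well-being at the two subsequent time points".

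The SAP describes the surgical plan as a post-randomisation variable. Under *Further analysis of primary endpoints generated prior to un-blinding* it says that stratifying on it is unsuitable for a primary outcome. It says nothing comparable about the concern category.

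**The concern.** Both stratifiers are fixed after the QPL has been mailed and the surgeon has been seen. Randomisation balances whole arms. It does not balance the people in each arm who happen to name the same concern.

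The QPL is meant to raise topics that patients would otherwise not raise. Its prompts cover options, recovery, serious complications and decisions if the patient cannot speak. Pilot patients in the QPL development paper said that it put new questions in their minds. A shift in which concern is named first, a day or two after the visit, is a plausible consequence. Respondents who name complications with the QPL could then be a different mix from those who name it without, and a within-category difference would combine that mix with any real effect.

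At stake is a supporting result that could be read as the QPL easing or worsening a given concern when it had only changed who named it. The SAP plans no table that would show whether such a shift occurred.

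**Working it through.** **Order of events.** QPL mailed, then visit (T0), then concern named and rated (T1), then the same concern re-scored (T2, T3). No MYCaW before exposure is described. The category is fixed at T1 and carried forward, so every within-category comparison, of means or of change, conditions on a post-exposure variable.

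**The plan's only MYCaW design figure.** The published protocol states 93% power for a difference of 0.5 × 1.26 = 0.63 points on the MYCaW well-being scale, at two-sided α = 0.025. A stepped-wedge calculation was run on the protocol's crossover table, with 40 surgeons, six waves, two patients per surgeon per wave, site-by-wave fixed effects, a surgeon random effect and 1.26 as the total SD. It gives 93.2%, 92.1% and 94.4% at intraclass correlations of 0.05, 0.10 and 0.30, so the figure reproduces. It applies to the whole cohort and the well-being scale. No figure is given for a within-concern comparison.

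**Artefact in the means when the QPL alters no rating.** Assume that everyone who would name the concern without the QPL still names it with the QPL. Let *s* be the share of the intervention group in that category that the QPL drew in, and *g* the mean rating of those drawn in minus that of the others. Then

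difference between arms = (1 − s)·m + s·(m + g) − m = s·g.

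The documents give neither *s* nor *g*. All values below are assumptions, with *g* scaled by the cited SD of 1.26 (itself a well-being figure, borrowed for the concern rating). Absolute size in points:

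| s | gap 0.25 SD | gap 0.5 SD | gap 1 SD |
|---|---|---|---|
| 0.1 | 0.03 | 0.06 | 0.13 |
| 0.3 | 0.09 | 0.19 | 0.38 |
| 0.5 | 0.16 | 0.32 | 0.63 |

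Worked example, all inputs assumed: 15% of controls name a concern, with mean rating 4.5, and the QPL leads a further 10% of patients, rating 3.5, to name it. The intervention mean is (15 × 4.5 + 10 × 3.5)/25 = 4.10, a difference of −0.40. With 5% drawn in it is (67.5 + 17.5)/20 = 4.25, or −0.25. With 15% it is (67.5 + 52.5)/30 = 4.00, or −0.50. With no shift in naming it is zero.

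**Simulation under the same null.** SD 1.26; 20% of controls and 30% to 40% of intervention respondents name the category; the tendency to name it correlates 0.3 to 0.5 with the rating. The artefact is −0.09 (30%, correlation 0.3) to −0.27 (40%, correlation 0.5). With correlation 0 it is nil. The negative sign follows from the assumed positive correlation.

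**Error rate.** Assume 130 respondents per arm in the planned-surgery cohort, treated as independent, and a nominal 5% test.

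- Smaller case: SE = 1.26 × √(1/26 + 1/39) = 0.319; 0.09/0.319 = 0.28; error about 6%.
- Larger case: SE = 1.26 × √(1/26 + 1/52) = 0.303; 0.273/0.303 = 0.90; error about 15%.

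**Change from T1.** If ratings are constant over time, change is zero in both arms whatever the mix, so a fixed gap in level cancels. Bias in change equals *s* times the difference in mean change between those drawn in and the others. The documents give nothing from which to size that difference.

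**The case against.** The defence has real substance.

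- **An all-concerns analysis is already written.** *Aim-2 primary outcomes [Regret, MYCaW]* specifies the patient's T1-T2 difference across all concern categories. A reader might infer that the plan has only the stratified comparison; it does not. Whether the earlier analysis survives is less clear. The modified plan presents itself as additional, but the stratified section argues that results under the pre-specified plan would be very hard to interpret, which can be read as replacing it.
- **The analysis is not primary.** The modified plan removes MYCaW from the primary endpoints, sets no α or power for this comparison, and specifies no p-value at the category step. This stands and limits the priority.
- **Change over time is the stated goal.** A reader might infer that the shift in means carries straight into the change analyses. It does not, because a fixed level gap cancels. Only differing trajectories would bias change.
- **A shift in naming is not shown.** It is inferred from the QPL's aims and the pilot. Clear presence or use of the QPL was noted in fewer than 20 transcripts, under 20/221 = 9% of intervention patients. Patients may still have read it at home, but the shift could be small.
- **The 0.63 figure is no yardstick.** It is tempting to express the artefact as a share of it. That figure is for the whole cohort on the well-being scale, not for the concern rating in a subgroup. That the table's top corner also equals 0.63 is a coincidence of multiplying 0.5 by 1.26.
- **Concerns are heterogeneous.** The SAP's objection to pooling, that worries about parking and about cancer are unlike, is fair and should be acknowledged.

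Blinded coding of concerns is no answer: it prevents coder bias but not a change in what respondents name.

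**Conclusion.** The point holds as one about what the within-concern comparisons can support. They condition on a variable fixed after exposure, and the SAP recognises that problem for the surgical plan but not for the concern category. Their means can differ by arm without any effect on an individual's rating, and their changes can be biased if respondents drawn in by the QPL have different trajectories.

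Size and direction are unknown. The range of about 0.03 to 0.6 points for the means rests on assumed shares of 10% to 50% and assumed gaps of 0.25 to 1 SD. The bias is zero if naming does not shift or is unrelated to the rating. The documents do not support a claim that the results will be biased, or by a stated amount. Because the analysis is supporting and an unstratified one is already specified, priority is modest.

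**What to change.** Three changes to the SAP:

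1. Report the distribution of first-concern category by assigned arm, for patients and family members separately, among all randomised respondents and not only those with a surgical plan. This shows whether the strata shifted, and is informative in itself.
2. Label the within-category comparisons, both means and changes, as descriptive, with no p-values or treatment-effect claims.
3. State that the all-concerns analysis in *Aim-2 primary outcomes [Regret, MYCaW]* is retained and is the source of any MYCaW effect claim. Report its T1 treatment difference alongside the change, because T1 is itself post-exposure. Acknowledge that pooled concerns are heterogeneous. As written, that analysis covers patients from T1 to T2 only.

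The cost is SAP wording and one table from concern codes already planned; no new data are needed. The downside is that the within-category results lose their status as treatment comparisons.

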The intervention effect will be tested in the framework of generalized linear mixed effects models^{42,43} with a treatment dummy variable, surgeon random effect and site-by-time dummy variables to control site-specific secular trends.

All models will be estimated and tested using SAS version 9.3 (SAS Institute, Cary, NC), specifically PROC MIXED and PROC NLMIX.

We do not plan to impute missing data if the rate of missingness is low. Currently, our rate of missingness is quite low: 97% of patients and 92% of family members have completed T1. For T2, 88% of patients and 86% of family members have completed the survey and for T3 87% of both patients and family members have completed their survey. We plan to exclude variables for which there is no response (rather than impute these variables). Although we have a small number of incomplete audio recordings, we will treat audio recordings where less than half of the encounter with the surgeon was captured (a total of 6 recordings) as completely missing and those with more than half recorded as complete. We will perform sensitivity analysis to test whether this small loss of data impacts our findings by comparing the outcomes with and without inclusion of audio recordings that are more than half complete.

Aim-1 primary outcomes [Question Counting, PEPPi-5]

Aim 1 has five primary outcomes and as such will be analyzed with a Type I error rate of $\alpha=0.01$.

For question counting, we consider four specific types of questions and evaluate them with ordinal categories:

- Number of OPTIONS questions asked by patients and family members (0, 1, 2+)
- Number of EXPECTATION questions asked by patients and family members (0, 1, 2+)
- Number of ADVANCE DIRECTIVES questions asked by patients and family members (0, 1+)
- Number of RISKS questions asked by patients and family members (0, 1, 2+)

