PEPPI-5 and HCCQ will be analyzed as continuous variables, based on the summary score of the entire survey (PEPPI-5 scale 0 – 25, HCCQ scale 1-7). We will first analyze all respondents (patients and family members) together, and then separate respondents into patient and family outcomes.

OPTION5 will be analyzed as a continuous variable with a scale that goes from 0 – 100 based on consensus coding of each T0 transcript. This is a surgeon/patient/family score that cannot be stratified by respondent. We will compare the average score between intervention and control for the entire cohort.

Secondary outcomes: Aim-2: treatment received, well-being [PROMIS]

Treatment received will be defined as patients who had at least one major operation during the study period (identified on completion of T3 chart review).

We will also analyze this outcome according to the following classification scheme to characterize the treatment plan after meeting with a surgeon:

1. Plan for major surgery (includes plans where surgery is the treatment decision but additional tests are required)
2. Plan to not have surgery (includes a decision that no surgery will be pursued or other clear treatment plan – e.g., chemo)
3. Plan is unclear – returning to discuss later, needs more information

PROMIS: These measures will be analyzed by respondent type (patient/family), and measures will be analyzed separately dependent on time of reporting (T2 and T3).

Patient: Impact of illness – positive: continuous scale: 8-20

Impact of illness – negative: continuous scale: 8-20

Family member: SF Global Health Physical Score: continuous scale raw score: 4-20

Family member: SF Global Health Mental Score: continuous scale raw score: 4-20

Patient and family member: Anxiety 4a: continuous scale: 4-20

We will then restrict the analysis to patients who plan to have major surgery, and family members' outcomes for family members whose dyad patient has a treatment plan for surgery. We will then adjust the analysis for patients who had a major complication with surgical intervention.

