Participating surgeons from these five centres routinely perform high-risk oncological or vascular surgery. Patients and family members are invited to participate as dyads. However, patients may participate alone while family members can only enrol with a corresponding patient. We will enrol patients in each surgeon's clinic according to a stepped wedge design implemented in six 4-month waves over a 24-month period (table 1). In wave 0, all patients will receive usual care. With each subsequent wave, 8 of the 40 enrolled surgeons will cross over into the intervention group. Once a surgeon has entered the intervention arm, all patients scheduled to see that surgeon in clinic to discuss a new surgical problem will receive the QPL intervention. We will audio-record the surgeon–patient conversation in clinic, and patients and family members will complete questionnaires at three subsequent predefined time points. In addition, we will perform qualitative interviews with a subset of participants who experienced serious postoperative complications.

Participants

Attending surgeons at participating sites who routinely perform high-risk vascular (peripheral, neurological or cardiovascular) or oncological operations on older patients will be invited to participate. Eligible patients are age 65 years and older with one or more chronic health conditions who have an outpatient consultation with a study-enrolled surgeon to discuss a new surgical problem. The surgical problem must be vascular or oncological in nature and could be treated with one of the 227 ICD-9-coded procedures our research group previously defined as high risk.⁵⁰ For each enrolled patient, we will approach one family member to participate who is present during the conversation with the surgeon in clinic. Eligible participants must be English-speaking or Spanish-speaking and able to converse with the surgeon without an interpreter (aside from Spanish-speaking participants who may use an interpreter), have self-reported visual acuity and literacy skills sufficient to read a newspaper, and be able to provide written informed consent. Patients who do not have a problem that can be potentially treated with

[figure not shown]

Figure 3 Screening, recruitment, enrolment and data collection points for patients in the control and intervention arms at each site.

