In qualitative interviews with a subset of participants who suffered a serious postoperative complication, we will use questions designed to explore the content of patient and family experience with perioperative conflict. The interview guide is structured around open-ended questions about perioperative events, including 'Tell me the story of your experience with surgery'.⁵⁸ The interviewer will follow up the respondents' narrative description with probing on the following domains: patient and family values and goals, decision making, interpersonal relationships (between surgeons and patients/family members, between treating physicians and between family members) and intrapersonal conflict (relating to post-treatment regret and self-blame). We will use feedback during concurrent coding and analysis to prompt additional questioning on emerging themes and trends.

Planned analyses

Quantitative analyses

Our primary analysis will compare the effectiveness of the QPL intervention relative to usual care in regard to patient engagement and patient psychological well-being. We will use an intention-to-treat analysis with all available data from participants based on group assignment. The intervention effect will be tested in the framework of generalised linear mixed-effects models^{59 60} with a treatment dummy variable, surgeon random effect and site-by-time dummy variables to control for site-specific secular trends. We will use linear mixed-effect models for continuous responses such as self-efficacy (PEPPI-5) and well-being (MYCaW), logistic random-effects models for binary responses such as post-treatment regret, and log-linear random-effect models for count-dependent variables such as the number and type of questions asked during the preoperative visit. For linear models, we will adjust for prespecified covariates to increase the statistical precision of our treatment effect estimation.

Our secondary analyses will examine other patient endpoints such as psychological well-being (PROMIS measures) and nature of treatment received. These analyses will also test for intervention effects in family member outcomes such as PEPPI-5, HCCQ, MYCaW, post-treatment regret and psychological well-being. We will use the generalised linear mixed modelling framework used in primary analyses for these outcomes. All models will be estimated and tested using PROC MIXED or PROC NLMIX in SAS V.9.3.

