We will perform additional analyses to test and quantify whether and to what extent the effect of the QPL intervention on patient engagement outcome measures is mediated by the presence of a family member during the visit with the surgeon. Exploratory analysis of family-reported outcomes will occur independently of patient-reported outcomes. To accomplish this, we will compare the indirect effect with the total effect in joint linear structural equation models for the endpoint and the mediator, including correlated random surgeon effects for each of the mediator and endpoint parts of the models. In addition, we anticipate treatment effect could vary across subpopulations defined by the following covariates: indication for surgery, patient comorbid illness and insurance status. Therefore, we will test the effect of treatment separately in subpopulations defined by these variables.

To decrease missing data, we limited the number of questions in the follow-up questionnaires and will provide a bonus incentive for participants who complete all three questionnaires. At the time of analysis, we will develop a comprehensive description of the missingness patterns and develop a plan for imputation that leverages the available data and concentrates on the data most heavily subject to missingness. If data are missing on predictor variables of interest, values will be imputed using multiple imputation techniques (ie, chained equations imputations).^{61 62} If dropout is substantial, we will again use

multiple imputation, including exploiting responses from the first two time points (day of clinic visit and 24–48 hours postvisit), to impute responses from the final two questionnaires, to maximise statistical efficiency and to minimise bias.

Sample size and power calculation

Each arm will contain 240 patients, for a total of 480 patient participants. Based on our prior work, we expect about 70%–80% of patients will have a family member present who will participate. Therefore, we estimate 384 family members from all sites will partake, although we will enrol up to 480 family members if all patients have a family member interested in participating. Assuming all enrolled patients enrol with a family member, the maximum number of all possible participants (surgeons, patients and family members) is 1000.

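### The pooled patient-and-family analyses of PEPPI-5 and HCCQ have no dyad term, so their standard errors are too small if the two members of a dyad score alike beyond the surgeon effect.

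*Combined protocol and SAP*

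**What the plan says.** The SAP section on Aim 1 secondary outcomes sets the order of analysis for PEPPI-5 and HCCQ: "We will first analyze all respondents (patients and family members) together, and then separate respondents into patient and family outcomes". It gives no model of its own.

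The model comes from the General Analysis Plan, which tests the intervention in generalized linear mixed models "with a treatment dummy variable, surgeon random effect and site-by-time dummy variables to control site-specific secular trends". The modified plan repeats this. The published protocol (Planned analyses, Quantitative analyses) extends it to secondary and family-member outcomes: "We will use the generalised linear mixed modelling framework used in primary analyses for these outcomes".

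The pairing is by design. The published protocol says under Setting and design: "Patients and family members are invited to participate as dyads". Under Participants it adds: "For each enrolled patient, we will approach one family member to participate who is present during the conversation with the surgeon in clinic". Both instruments are given at T1, 24-48 hours after that visit.

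Neither document gives a dyad random effect, a dyad-level covariance or a cluster-robust variance for the pooled analysis. Dependence is handled elsewhere: MYCaW over time has a patient-level effect, the stratified MYCaW change analysis has a respondent-level effect, and regret is reduced to one value per dyad.

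**The concern.** Most patients in the pooled data contribute two records, their own and a relative's, both following the same conversation with the same surgeon. A model with only a surgeon random effect treats these two records as no more alike than records from two different patients of that surgeon at that site and time. If they are more alike, the model counts more independent information than there is, and the pooled interval is too narrow and the p-value too small.

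The SAP repeats the restricted analyses for all secondary outcomes, so the gap carries into those pooled re-runs.

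Pooling also raises a question of composition. Under Additional important outcomes, the SAP expects that the question list may prompt patients to bring a relative. If the intervention arm then holds a larger share of family records, and relatives score differently from patients, a pooled comparison without a respondent-type term mixes that shift into the treatment effect.

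**Working it through.** **Inputs.**
- Published protocol: 40 surgeons, six waves and the Table 1 crossovers; 2 patients per surgeon per wave, which matches 480/(40 x 6) = 2 (the SAP's Study design allows up to 3); 70-80% of patients with a participating relative; between-surgeon variance 5% (found at one site) to 30% (worst case) of the total; PEPPI-5 SD 4.3; two-sided alpha 0.025 for the power figures.
- SAP: 222/221 patients; T1 completion 97% of patients and 92% of family members.
- Assumed: rho, the correlation of dyad members' residuals given surgeon, site and wave.

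**Step 1. The plan's own figure.** No figure is stated for the pooled analysis. The published protocol gives 93% power at d = 0.5 and 82% at d = 0.425 for one rating per patient. Generalized least squares with a surgeon intercept and site-by-time effects gives SE(d) = 0.134 at 5% surgeon variance and 0.1305 at 30%. With power = Phi(d/SE - 2.241):
- d = 0.5: Phi(3.731 - 2.241) = 93.2% and Phi(3.831 - 2.241) = 94.4%.
- d = 0.425: 82.4% and 84.5%.

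The 93% is reproduced at both values, and the 82% at 5% surgeon variance. The design is therefore represented adequately.

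**Step 2. Closed-form check.** Let f be the share of patients with a relative. Ignoring surgeon effects, true variance over model variance is

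[(1 - f) + 2f(1 + rho)]/(1 + f) = 1 + rho x 2f/(1 + f),

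where 2f/(1 + f) is 1.4/1.7 = 0.82 at f = 0.7 and 1.6/1.8 = 0.89 at f = 0.8. The shortfall of the reported SE is 1 - 1/sqrt(ratio):
- rho 0.1: ratio 1.082-1.089, shortfall about 4%.
- rho 0.3: ratio 1.247-1.267, shortfall 10-11%.
- rho 0.5: ratio 1.412-1.444, shortfall 16-17%.

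**Step 3. In the actual design.** The data set has about 745 ratings, from about 430 patients and their relatives (80% participation, T1 completion as above), with a respondent-type indicator in the model. The surgeon-only model's variance components were taken from expected REML, and its model-based SE was compared with the true sampling SE of the same estimator. Type I error = 2[1 - Phi(1.96 x SE ratio)]; for example, 1.96 x 0.892 = 1.748 gives 8.0%.

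| rho | Reported/true SE, surgeon variance 5% | Type I error | Reported/true SE, surgeon variance 30% | Type I error |
|---|---|---|---|---|
| 0 | 1.000 | 5.0% | 1.000 | 5.0% |
| 0.1 | 0.968 | 5.8% | 0.961 | 6.0% |
| 0.2 | 0.938 | 6.6% | 0.925 | 7.0% |
| 0.3 | 0.910 | 7.5% | 0.892 | 8.0% |
| 0.5 | 0.857 | 9.3% | 0.835 | 10.2% |

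At 70% participation, which was run at rho 0.3 only, the ratios are 0.923 and 0.908, with type I error 7.1% and 7.5%.

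**Step 4. On the PEPPI-5 scale** (SD 4.3, surgeon variance 30%, 80% participation), the 95% half-width is 1.96 x 4.3 x SE:
- rho 0.3: reported 8.428 x 0.1057 = 0.89 points; true 8.428 x 0.1184 = 1.00.
- rho 0.5: reported 8.428 x 0.1050 = 0.89 points; true 8.428 x 0.1257 = 1.06.

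With the dyad covariance modelled at rho 0.3, the SE is 0.1177 (half-width 0.99), against 0.1378 for patients alone. Pooling still gains precision once the pair is modelled.

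**The case against.** The strongest reply is that this is an omission and not a stated wrong model. The secondary-outcome section names no model, and the SAP adds patient- or respondent-level effects for MYCaW that the general plan does not list, so the general list is not exhaustive. This stands in part: an analyst could add a dyad term without contradicting the text. But no sentence calls for one, and the framework that the published protocol extends to these outcomes does not contain one.

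Second, a reader might infer that the pooled intervals are certainly too narrow. The documents do not support that. It requires rho above zero, and rho is not given. A positive value is plausible for HCCQ, where both people rate the surgeon's support at one visit. It is less obvious for PEPPI-5, which measures each respondent's own confidence. The surgeon effect already absorbs the likeness shared by all of a surgeon's patients.

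Third, a reader might carry the figures over to MYCaW, where the SAP says: "We will first categorize participants (both patients and family members) by the primary (first) concern expressed". They do not carry over. No model is stated for that comparison of means, and a patient and relative enter the same comparison only if their primary concerns fall in the same category.

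Fourth, a reader might take the published protocol to rule out pooling, because it says: "Exploratory analysis of family-reported outcomes will occur independently of patient-reported outcomes". That sentence concerns exploratory analysis and sits in the paragraph on mediation by family presence. It does not settle how the main PEPPI-5 and HCCQ analyses are done.

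Finally, the stakes are limited. Both are secondary outcomes under the modified plan, which itself regards a PEPPI-5 difference as of no clinical meaning because of ceiling effects. The pooled analysis is the first performed; nothing says that it is the headline result. All of this stands and limits the weight of the point.

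**Conclusion.** The point holds as a gap in the pooled PEPPI-5 and HCCQ models. Followed as written, the plan ignores any within-dyad correlation beyond the surgeon effect. Across 70-80% family participation, and taking both calculations together, the reported SE is too small by about 3-4% at rho 0.1, about 8-11% at rho 0.3 and about 14-17% at rho 0.5. The corresponding type I error is about 6%, 7-8% and 9-10% at a nominal 5%. There is no error at rho 0. These results rest on the assumed rho, on surgeon variance of 5-30%, and on reading the general framework as the model for these outcomes.

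A reader who inverts the ratio could quote a shortfall of 19-20% at rho 0.5. That is how much larger the true SE is than the reported one in the closed form (1.19-1.20); the reported SE is 16-17% too small (1 - 1/1.19 to 1 - 1/1.20).

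The separate patient and family analyses have one record per dyad and are not affected. Nor are the modified plan's primary endpoints: question counts are one set per consultation, and regret is one value per dyad.

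**What to change.** In the SAP section on Aim 1 secondary outcomes, state that the pooled PEPPI-5 and HCCQ models, and their restricted re-runs, include a dyad random intercept nested in surgeon and a fixed effect for respondent type (patient or family member). In PROC MIXED this is one further RANDOM statement and one covariate; patients without a relative form dyads of one. For the pooled MYCaW comparison by concern category, use the same dyad term where both members fall in the same category. Write this in before unblinding.

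The cost is a sentence of SAP text, a line of code and slightly wider pooled intervals: on the PEPPI-5 scale about 0.99 instead of 0.89 points half-width at rho 0.3. If rho is in fact near zero, little is lost. An alternative is to name the separate patient and family analyses as the main ones and present the pooled result as supportive.
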